Digitalized pathology slide: hematoxylin and eosin (HE) slides coming from diagnostic biopsy or surgical specimens will be digitalized and collected in a pre-defined folder. Both slides from primary tumor and from metastatic sites that underwent biopsy assessment will be collected, if available. If more than one metastatic biopsy has been performed during the course of patient's disease, all the HE slides should be collected, if available. If a patient did not undergo neoadjuvant treatment, diagnostic biopsy of the breast or surgical tumor slide could be collected equivalently; otherwise, the diagnostic biopsy performed before treatment initiation should be taken.

(4) Translational sub-study

Objectives and endpoints of the sub-study

Primary objective:

- To find the mutational status of a gene, or a subset of genes, associated with differential survival outcomes (rwPFS, TTNT-D, TTC-D and OS) of HR+/HER2- aBC patients treated with first-line ET+CDK4/6i;
- To find transcriptomic differential gene expression, or differential expressed pathways, associated with differential survival outcomes (rwPFS, TTNT-D, TTC-D and OS) of HR+/HER2- aBC treated with first-line ET+CDK4/6i.

Secondary objectives:

- To test the effect of PAM50 intrinsic subtype on survival outcomes (rwPFS, TTNT-D, TTC-D and OS) of HR+/HER2- aBC patients treated with first-line ET+CDK4/6i;
- To combine genomics and transcriptomics features with clinical data and radiomics and pathomics features, to build a model able to predict prognosis of HR+/HER2- aBC patients treated with first-line ET+CDK4/6i;
- To test the association between agnostic features included in radiomics model and transcriptomic pathways and mutational status.

Study Population

The same inclusion and exclusion criteria adopted for the RWD sub-study will be adopted for the present sub-study, for the only exception of the following inclusion criterion:

Availability of adequate tumor sample (see Data Collection below) from biopsy of metastatic sites and/or from primary tumor biopsy and/or from surgery specimen.

Data collection

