For the "Translational sub-study" purposes, tumor samples related to patients enrolled in the RWD sub-study will be considered. If multiple tumor samples are available, the ones to be used for the study has to be chosen as specified in the section "Translational sub-study". Tumor materials have to be shipped to the Sponsor center at the moment of the conduction of translational analyses, attributing the same pseudonymized code used for the other sub-study. The remaining unused tumor tissue will be sent back to the pathology laboratory at the end of the study.

Statistical considerations

Statistical design

Based on pivotal trials showing a statistically significant OS advantage for ribociclib and abemaciclib, but not for palbociclib in the endocrine resistant setting, and clinically meaningful OS advantage for ribociclib and abemaciclib, but not for palbociclib in the endocrine sensitive setting, we will hypothesize a difference of 20% in terms of OS between ribociclib versus palbociclib and between abemaciclib and palbociclib. To detect this difference with 80% power with a two-sided alpha error of 0.05, a sample size of 3258 patients reaching 977 OS events will be required. The prognostic role of CDK4/6i drug will be weighed for clinically and biologically relevant characteristics.⁸⁹

Since the number of patients enrolled in the other sub-studies depends on the sample size of the RWD sub-study, no formal statistical calculation has been performed for 2 to 5 PALMARES-2 sub-studies.

Statistical methods

Version 1.1, 01Aug2024

Standard descriptive statistics will be used to describe clinical and biological patients' characteristics. The median and interquartile range (IQR) were reported for continuous variables. Categorical variables were summarized as percentages of available data. To evaluate differences, in terms of clinic-pathological characteristics, among different CDK4/6i groups, we will use the Kruskal-Wallis Rank Sum test for

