continuous variables and the Chi-square and Fisher exact tests for categorical variables. Unpaired t-test will be used to compare numeric variables, at baseline and different timepoints. Classic survival analysis methods will be used to evaluate patient survival outcomes and survival curves will be obtained through the Kaplan–Meier method. Follow-up times will be estimated using the reverse Kaplan–Meier method. Multivariable analysis will be performed through Cox regression modeling to estimate the effects of covariates. To homogenize patients' characteristics among treatment groups, additional adjustment techniques will be eventually used, such as propensity score matching (PSM) and inverse probability of treatment weighting (IPTW). Estimated weights will be then incorporated into a weighted Cox regression model to estimate rwPFS. Area Under the ROC Curve (AUC) values of the models will be calculated using the Caret and pROC R package and compared using Delong's test.

Patients with missing outcome data will be excluded from the analysis. Covariates whose values will be missing in less than 20% were imputed by using the median or the mode value (for numerical or categorical variables, respectively), while covariates with missing values exceeding 20% will be excluded from the present analysis. 90 All statistical tests will two-tailed, and a p value (P) <0.05 was considered as significant. Statistical analyses will be performed using R software and R Studio (version 4.1.2).

Image omics and model generation methodology

Radiomics Methodology

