variants, and copy number variations (CNVs), including both copy number gains and losses, across ~500 genes. The panel will include, but will not be limited to, genes involved in DNA repair systems (e.g. *BRCA1*, *BRCA2*, *PALB2*, *CHEK2*, *ATM*), PIK3CA pathway (e.g. *PIK3CA*, *AKT1*, *PTEN*), estrogen receptor (e.g. *ESR1*). It also allows the quantitative evaluation of tumor mutational burden (TMB) and the analysis of the microsatellite instability (MSI) status.⁹⁷

Transcriptomic analyses

After cellular RNA extraction, RNA quality check and preparation of libraries, RNA will be sequenced with NovaSeq 6000 System. Counts will be analyzed to dissect differential gene expression both at single gene level – through differential gene expression analysis (i.e, Deseq2 method) – and at pathway level – through Gene Set Enrichment Analysis (GSEA), Over Representation Analyses (ORA) and Gene Set Variation Analysis (GSVA).(30,31) The pathway-level analysis will be carried out using the Bioconductor packages fgsea, gsva, and clusterprofiler, taking advantage of HALLMARK, KEGG, and REACTOME gene sets available from GSEA Molecular Signatures Database (http://www.gsea-msigdb.org/gsea/msigdb/collections. jsp). Intrinsic subtypes will be assessed through Absolute Intrinsic Molecular Subtyping (AIMS) algorithm. ^{98–100}

Study duration

Patient enrollment and data collection will start upon approval of the study protocol by the competent ethics committee. All consecutive HR+/HER2- aBC patients treated with first-line ET plus CDK 4/6 inhibitors as per clinical practice in the time interval between January 2016 and December 2030 will be enrolled. The collection and the update of clinical data, medical images and biological samples will continue for an expected duration of 10 years from the enrollment of the last patient. The clinical data, medical images and data obtained from the biological samples will be retained for further 10 years after the end of the study, while the biological samples will be returned to the pathology departments of the Center of origin at the end of the analyses foreseen in the protocol.

Ethical considerations

This study will be conducted according to the Declaration of Helsinki and in compliance with ethical principles regarding human research.

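### One of three unranked pathway routes in sub-study 4, fgsea in its standard gene-sampling use, gives p-values too small to support a claim of association with survival at p<0.05

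*Protocol*

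**What the plan says.** Section (4), Translational sub-study, lists two primary objectives. The first concerns mutational status. The second reads "To find transcriptomic differential gene expression, or differential expressed pathways, associated with differential survival outcomes (rwPFS, TTNT-D, TTC-D and OS" and so on, so pathways are one alternative within it.

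The Transcriptomic analyses part of Biological analyses methodology sets out the tools. Gene-level work is done "through differential gene expression analysis (i.e, Deseq2 method"). Pathway-level work is done "through Gene Set Enrichment Analysis (GSEA), Over Representation Analyses (ORA) and Gene Set Variation Analysis (GSVA"). On software: "The pathway-level analysis will be carried out using the Bioconductor packages fgsea, gsva, and clusterprofiler". The gene sets come from three curated collections: HALLMARK, KEGG and REACTOME. The text does not say which of the three methods decides, what statistic ranks the genes, or whether genes or patients are permuted.

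Statistical methods sets one threshold for everything: "All statistical tests will two-tailed, and a p value (P) <0.05 was considered as significant". Statistical design adds that "no formal statistical calculation has been performed for 2 to 5 PALMARES-2 sub-studies", so no patient number is available for this sub-study.

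**The concern.** The objective asks a question about patients: is a pathway's expression linked to how long they live, or remain free of progression, a next treatment or chemotherapy? The matching null hypothesis is no association across patients.

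A preranked enrichment test answers a different question. It takes one ranked gene list and asks whether the members of a set sit closer to one end than a random set of equally many genes would. That null treats genes as independent draws. Genes in curated pathways tend to be co-expressed, so when outcome is pure noise, chance moves many of them in the same direction, the set clusters at one end, and the test rejects. More patients do not help: under the null, the correlation between gene-level statistics equals the correlation between the genes, whatever the sample size.

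At stake is what a significant pathway means. If the named package is run in its usual way and judged by the general threshold, the p-value does not measure evidence of association with survival. This is separate from multiplicity, because each p-value is already wrong before any adjustment.

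**Working it through.** **Inputs from the protocol.** The tools, the gene-set collections and the two-sided 0.05 level.

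**Assumptions, because the protocol gives no values.** Set size m, mean within-set correlation ρ, 200 patients, about 60% events, and gene sampling as the fgsea null.

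**Closed form.** For m gene statistics with unit variance and mean correlation ρ, the variance of their mean is [1+(m−1)ρ]/m. Gene sampling uses 1/m. The true rejection rate at nominal 5% is therefore

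2·{1 − Φ(1.96/√[1+(m−1)ρ])}.

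- m=100, ρ=0.05: 1+99×0.05 = 5.95; √5.95 = 2.44; 1.96/2.44 = 0.80; rate 42.2%.
- m=15, ρ=0.01: 1+14×0.01 = 1.14; √1.14 = 1.07; 1.96/1.07 = 1.84; rate 6.6%.

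**Simulation.** 5,000 genes, 200 patients, censored survival unrelated to every gene, genes ranked by a Cox score statistic, and the weighted running-sum enrichment statistic referred to random gene sets of equal size. There were 150 datasets with four sets per size, so 600 tests per cell. The Monte Carlo standard error at 5% is √(0.05×0.95/600) = 0.9 percentage points. Entries are simulated rejection rates at p<0.05 (closed form in brackets). The last column is the share of datasets with at least one false pathway among 12 after Benjamini-Hochberg at 5%.

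| ρ | m=50 | m=100 | m=200 | any false after BH |
|---|---|---|---|---|
| 0 | 5.0% (5.0) | 5.0% (5.0) | 5.2% (5.0) | 0% |
| 0.01 | 12.3% (10.8) | 14.2% (16.5) | 21.8% (25.7) | 15% |
| 0.05 | 27.0% (29.1) | 36.8% (42.2) | 50.0% (55.4) | 78% |
| 0.10 | 36.0% (42.0) | 52.3% (55.3) | 63.0% (66.8) | 95% |
| 0.20 | 53.8% (55.1) | 61.7% (66.7) | 68.5% (75.9) | 100% |

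The nominal level is recovered at ρ=0, so correlation is the cause. The closed form is for a set mean and not for the running sum, which is why the two agree only approximately.

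**Where the inflation is mild.** The closed form gives 6.6% and 8.3% for m=15 at ρ=0.01 and 0.02, and 7.9% for m=50 at ρ=0.005. It rises to 13.3% and 20.6% for m=15 at ρ=0.05 and 0.10.

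**Same data, patients as the unit.** Shuffling patients instead of genes gave 3.5% to 5.8% over all cells. A per-patient mean-of-genes score tested against outcome gave 4.0% to 6.5%.

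**Two cross-checks.**
- A separate simulation (10,000 genes, 50 sets of 100, 200 patients, about 50% censored, 40 runs) gave 5%, 21%, 38%, 50% and 62% at ρ = 0, 0.02, 0.05, 0.10 and 0.20. In it, ORA rejected in 4% to 10% of null sets.
- Ranking genes by a two-group comparison instead of a Cox statistic, for sets of 100, gave 6.5%, 22.8%, 39.0% and 52.7% at ρ = 0, 0.02, 0.05 and 0.10. The result does not hinge on the Cox ranking.

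**The case against.** The strongest reply is that the faulty analysis is inferred. The protocol does not chain DESeq2 into fgsea, does not mention a preranked run and does not state the permutation unit. A run that permutes patients would remove the problem, and such settings are often left to an SAP, which is not at hand. That stands as a limit: the point holds for the standard use of the named package, not for every possible use. It does not dispose of the point, because the protocol itself names the package and applies p<0.05 to every test, and an SAP that followed both in the usual way would inherit the error.

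It can also be said that the objective is one of discovery, that no pathway test is labelled confirmatory, and that GSVA scores and Cox regression are both already planned. All true. But nothing gives the GSVA route precedence, so an enrichment hit alone would still count.

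A reader might infer that the whole pathway part depends on fgsea, or that half of the sub-study's primary objective is compromised. The document supports neither. fgsea is one of three named routes, and pathways are an alternative, joined by an or, inside the second of two objectives.

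Finally, the calculations use neither the DESeq2 statistic nor GSVA itself. The two-group check eases the first gap. The second remains.

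**Conclusion.** The concern holds in limited form. If fgsea is run with gene sampling and judged at p<0.05, its p-values are not valid evidence that a pathway is associated with survival. For sets of 50 to 200 genes with within-set correlation of 0.05 to 0.20, about 27% to 69% of null pathways would be called significant, and Benjamini-Hochberg does not correct this. For very small or barely correlated sets the rate is about 6% to 8%. ORA also samples genes, with less inflation in the one simulation that examined it.

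The direction follows from the method. The size rests on assumed set sizes and correlations, since the protocol gives neither. The near-nominal error rate with patients as the unit was shown for a mean-of-genes score and for patient permutation, not for GSVA. The effect is confined to one strongly affected route out of three in one sub-study, and has no bearing on the overall-survival comparisons of sub-study 1.

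**What to change.** In Transcriptomic analyses, add two statements.

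1. Any claim that a pathway is associated with rwPFS, TTNT-D, TTC-D or OS rests on a test with patients as the sampling unit: the planned per-patient GSVA score in a Cox model, or an enrichment test that permutes patients or corrects for inter-gene correlation (for example ROAST or CAMERA).
2. Gene-sampling fgsea and ORA p-values are descriptive and exempt from the general p<0.05 rule.

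The calibration of the GSVA score should be confirmed by permuting outcomes across patients, because it was not checked here.

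The cost is two sentences and a few lines of R, with no new patients, samples or data. The downside is that fewer pathways will be declared significant.
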